3.1.1. All Randomized Analysis Set

All Randomized Analysis Set includes all subjects who were randomized in the study. This is the primary analysis set for by-subject listings.

3.1.2. Full Analysis Set

The Full Analysis Set (FAS) includes all subjects who were randomized and received at least one dose of study drug (filgotinib, lanraplenib or placebo). This is the primary analysis set for efficacy analyses.

3.1.3. Safety Analysis Set

The Safety Analysis Set includes all subjects who received at least 1 dose of study drug. This is the primary analysis set for safety analyses.

3.1.4. Per-Protocol Analysis Set

The per-protocol analysis will not be performed due to a limited number of subjects in the study.

3.1.5. Pharmacokinetic Analysis Set

The Pharmacokinetic (PK) Analysis Set will include all randomized subjects who took at least 1 dose of study drug and have at least 1 non-missing post-dose concentration value reported by the PK laboratory. This is the primary analysis set for all PK analyses. Within the PK Analysis Set, those subjects with PK exposure data successfully derived from the population PK modeling (if applicable) will be included in the analyses related to PK exposure.

3.1.6. Biomarker Analysis Set

The primary analysis set for biomarker analyses will be the Biomarker Analysis Set, which includes all randomized subjects who received at least one dose of study drug and have at least one baseline measurement available for the specific parameter of interest.

3.2. Subject Grouping

In the FAS and PP Analysis Set, subjects will be grouped according to the treatment to which they were initially randomized at Study Day 1. For the analyses based on the Safety Analysis Set, subjects will be grouped according to the actual treatment that they received. The actual treatment received will be considered to differ from the randomized treatment only when subject's actual treatment differs from randomized treatment for the entire treatment period.

For the analysis of the placebo-controlled period (up to week 12), subjects will be presented by three treatment groups:

- Filgotinib 200 mg
- Lanraplenib 30 mg
- Placebo

For the analyses for the entire study duration, subjects will be grouped into five treatment groups as specified in [Table 2](#).

Table 2. Treatment Groups for the Entire Study Duration

Lanraplenib 30 mg	Lanraplenib 30 mg from Study Day 1
Filgotinib 200 mg	Filgotinib 200 mg from Study Day 1
Placebo/Lanraplenib 30 mg	Placebo up to Week 12 and lanraplenib 30 mg after Week 12
Placebo/Filgotinib 200 mg	Placebo up to Week 12 and filgotinib 200 mg after Week 12
Placebo	Placebo group with study drug withdrawn prior to or at Week 12 (did not receive drug assigned at Week 12)

For the PK analyses, subjects will be grouped according to the actual treatment they received.

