1.3. Sample Size and Power

With a sample size of 50 subjects (20 in each active treatment arm and 10 in the placebo arm), there is a 79% power to detect a 2 point difference between each active arm and the placebo arm in the primary endpoint, change from baseline in CLASI activity score at week 12, using a 2-sided 0.1 level test. This power calculation assumes a common standard deviation of 2 and a 10% drop-out rate per arm.

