7. SAFETY ANALYSES

The safety analyses will be performed for the placebo-controlled treatment period up to Week 12, up to Week 24, and for the entire study duration. Analyses for these treatment periods will be presented by the treatment groups specified in Section 3.

For the analyses of adverse events that include data after Week 12 the exposure-adjusted analyses will be presented.

For the AEs, laboratory abnormalities and concomitant medication data, the collection/start date will be used to determine which reporting period the record belongs to. For other parameters, the nominal visits will be used.

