7.1.5. Treatment-Emergent Adverse Events

7.1.5.1. Definition of Treatment-Emergent Adverse Events

Treatment-emergent adverse events (TEAEs) of the entire study duration are defined as 1 or both of the following:

- Any AEs with an onset date on or after any study drug start date and no later than 30 days after permanent discontinuation of any study drug
- Any AEs leading to premature discontinuation of study drug.

TEAEs up to Week12/24 are defined as 1 or both of the following:

- Any AEs with an onset date on or after Day 1, prior to start of Week 12/24 treatment and no later than the day before the Week 12/24 treatment start date. For subjects who discontinued treatment prior to Week 12/24 visit, any AEs with an onset date on or after the study drug start date and no later than 30 days after permanent discontinuation of study drug
- Any AEs leading to premature discontinuation of study drug prior to first Week 12/24 dosing

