7.2.3. Liver-related Laboratory Evaluations

Liver-related abnormalities after initial study drug dosing will be examined and summarized using the number and percentage of subjects who were reported to have the following laboratory test values for postbaseline measurements:

- Aspartate aminotransferase (AST): (a) > 3 times of the upper limit of reference range (ULN); (b) $> 5 \times$ ULN; (c) $> 10 \times$ ULN; (d) $> 20 \times$ ULN
- Alanine aminotransferase (ALT): (a) $> 3 \times$ ULN; (b) $> 5 \times$ ULN; (c) $> 10 \times$ ULN; (d) $> 20 \times$ ULN
- AST or ALT: (a) $> 3 \times$ ULN; (b) $> 5 \times$ ULN; (c) $> 10 \times$ ULN; (d) $> 20 \times$ ULN
- Total bilirubin: $> 2 \times$ ULN
- Alkaline phosphatase (ALP) $> 1.5 \times$ ULN
- AST or ALT $> 3 \times$ ULN and total bilirubin: (a) $> 1.5 \times$ ULN; (b) $> 2 \times$ ULN

The summary will include data from all postbaseline visits on active treatment up to 30 days after the last dose of study drug. For individual laboratory tests, subjects will be counted once based on the most severe postbaseline values. For both the composite endpoint of AST or ALT and total bilirubin, subjects will be counted once when the criteria are met at the same

postbaseline visit date. The denominator is the number of subjects in the Safety Analysis Set who have nonmissing postbaseline values of all relevant tests at the same postbaseline visit date.

The analyses will be presented for the placebo-controlled period and entire study period.

A listing of subjects who met at least 1 of the above criteria will be provided.

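### In entire-study adverse-event analyses, the Placebo column holds only placebo subjects who stopped drug by Week 12, and the two switch columns mix placebo-time and active-time events

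*SAP*

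**What the plan says.** SAP 3.2 has two grouping schemes. Up to Week 12 there are three groups, and the whole placebo arm is one of them. Beyond that: "For the analyses for the entire study duration, subjects will be grouped into five treatment groups", listed in Table 2. Two are the active arms from Day 1. Two are sequence groups, *Placebo/Lanraplenib 30 mg* and *Placebo/Filgotinib 200 mg*. The fifth, *Placebo*, is "Placebo group with study drug withdrawn prior to or at Week 12", with the added condition that the drug assigned at Week 12 was not received.

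SAP 7 states that safety analyses will be done for the period up to Week 12, "up to Week 24, and for the entire study duration", using the groups in Section 3. Adverse-event analyses with data after Week 12 are to be exposure-adjusted. The entire-study TEAE definition in SAP 7.1.5.1 begins "Any AEs with an onset date on or after any study drug start date", so for a placebo subject the window opens on placebo.

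SAP 7.1.6 plans the TEAE tables for up to Week 12 and for Weeks 12-48, and makes an overall entire-study summary optional. SAP 7.2.3 says of the liver tables: "The analyses will be presented for the placebo-controlled period and entire study period". The same section limits the data to post-baseline visits on active treatment.

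**The concern.** A column headed *Placebo* in an entire-study safety table will be read as the control. Here it is defined by an outcome: everyone in it stopped study drug by Week 12. The placebo subjects who tolerated placebo and went on to active drug, probably most of the arm, are elsewhere.

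The events those subjects had on placebo are added to the events they had later on active drug. A rate for either sequence column is therefore neither a placebo rate nor a drug rate. The SAP does not say which exposure is the denominator, and SAP 4.2.1 derives both total exposure and active-treatment duration.

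The events of special interest in SAP 7.1.7 include thrombosis, malignancy and serious infection. With 50 subjects these may be few, so the column in which a single event is counted can change how the table is read.

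**Working it through.** **1. The plan's own figure.** Inputs from SAP 1.3: arm sizes of 20, 20 and 10; "there is a 79% power to detect a 2 point difference between each active arm and the placebo arm"; a two-sided level of 0.1; SD 2; 10% drop-out per arm. After drop-out the arms are 18 and 9.

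- SE = 2 × √(1/18 + 1/9) = 0.816
- Power ≈ Φ(2/0.816 − 1.645) = Φ(0.805) = 78.95%, which matches 79%. A noncentral t gives 76.96%.

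The power is not in dispute. The check shows that the plan's 10% means 10 placebo subjects become 9.

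**2. Size of the *Placebo* column.** Assume that drop-out means stopping drug by Week 12, independently between subjects, with probability d. Expected number = 10d; P(empty) = (1 − d)^10.

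| d | Expected number | P(empty) |
|---|---|---|
| 5% (assumed) | 0.5 | 60% |
| 10% (SAP 1.3) | 1 | 35% |
| 20% (assumed) | 2 | 11% |
| 30% (assumed) | 3 | 3% |

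**3. Where the placebo time sits.** With one such subject, nine switchers contribute 9 × 12 = 108 placebo weeks to the sequence columns. If the remaining subject contributes 0, 6 or 12 weeks, the sequence columns hold 108/108 = 100%, 108/114 = 95% or 108/120 = 90% of all placebo time.

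**4. Placebo share within columns.**

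- Sequence columns, switcher completing 48 weeks: 12/48 = 25%.
- Sequence columns, analysis up to Week 24 if grouped by Table 2: 12/24 = 50%.
- Active-from-Day-1 columns: 0 of 20 × 48 = 960 subject-weeks per arm.

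**5. Effect on a rate in a sequence column.** Set the placebo rate to 1, the active rate to R and the placebo share to a, with constant rates. All events are in the numerator, as SAP 7.1.5.1 implies.

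- Denominator total exposure: a + (1 − a)R
- Denominator active duration only: R + a/(1 − a)

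| Assumed R | Denominator | a = 25% | a = 50% |
|---|---|---|---|
| 2 | total exposure | 1.75 | 1.50 |
| 2 | active duration | 2.33 | 3.00 |
| 3 | total exposure | 2.50 | 2.00 |
| 3 | active duration | 3.33 | 4.00 |

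The direction of the error depends on a denominator that the SAP does not state.

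**6. Which analyses are touched.**

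- TEAE tables up to Week 12 and for Weeks 12-48 (7.1.6): split at the switch, not affected.
- Laboratory abnormalities (7.2.2.1, 7.2.2.3): shown by placebo-controlled and active period, with switchers re-baselined at first active dose. Not affected.
- Entire-study AE analyses (7, 7.1.5.1): affected. Section 7 says they will be done, while 7.1.6 makes the overall TEAE summary optional.
- Up to Week 24 (7, 7.1.5.1): period defined, grouping not. Table 2 is one reading. Extending the three-group scheme is the other, and it would put up to 12 weeks of active drug under *Placebo*.
- Liver tables (7.2.3): restricted to visits on active treatment, which would leave *Placebo* with no data. That conflicts with presenting the placebo-controlled period.

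**The case against.** The best defence is that the plan already protects the comparison that matters. The Week 12 tables keep the whole randomised placebo arm. No concurrent placebo group exists after Week 12 by design, so no later table could be a randomised comparison. The main TEAE and laboratory-abnormality tables are split by period, the overall entire-study TEAE summary is only optional, and Table 2 prints its definition openly and counts each subject once. Nothing in the SAP formally uses the residual *Placebo* column as a control. All of this stands, and it limits the severity.

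A reader might infer something stronger: that the active columns are diluted with placebo time, or that all later safety tables, including laboratory and liver, are biased. The documents do not support that. The mixed columns carry *Placebo/* in their names, and the two active-from-Day-1 columns contain no placebo time. The laboratory-abnormality tables are split. Read literally, the liver section excludes placebo-time values, so its defect is an internal conflict. For Week 24 the demonstrable fault is a missing definition; a biased table follows only if Table 2 is applied.

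The defence does not rescue the entire-study AE analyses. An openly defined column is still selected on outcome, and exposure adjustment does not separate time on two treatments.

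**Conclusion.** The point holds for entire-study AE analyses grouped by Table 2. The *Placebo* column is a remnant of about 1 subject in 10, empty with probability 35%, and cannot serve as a control. The sequence columns mix treatments, with a 25% placebo share for a switcher completing 48 weeks. The Week 24 analysis lacks a grouping, and Table 2 would give it the same problem at 50%.

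The column size rests on applying the power calculation's drop-out to drug withdrawal by Week 12. Table 2 speaks of study drug, and Protocol 3.5.2 lets such subjects continue visits, so they have not necessarily left the study. The rate illustrations rest on assumed constant rates and assumed ratios of 2 and 3. The fault in the column definitions depends on none of these.

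Severity is minor to moderate, because the randomised Week 12 comparison is intact.

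**What to change.** For every AE or AE-of-special-interest analysis that spans Week 12 (entire study and up to Week 24), attribute events and exposure to the treatment being taken at onset:

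- **Placebo:** all placebo-randomised subjects, from Day 1 to the day before the first active dose, or to last dose + 30 days if never switched.
- **Each active drug:** the original arm from Day 1, and switchers from their first active dose, shown separately and pooled.
- **Denominator:** the exposure that matches each column. The first-active-dose date (SAP 3.8.1) and active-treatment duration (SAP 4.2.1) are already derived. For switchers, placebo exposure is total minus active duration, for example 48 − 36 = 12 weeks.

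State this as the grouping for the Week 24 analysis. Keep Table 2 for disposition and listings, and relabel its last row, for example as *Placebo, not switched*. In SAP 7.2.3, reconcile the restriction to active treatment with the two periods to be presented.

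The cost is SAP wording and table shells, with no new data. Switchers will appear in two columns, which needs a footnote. Placebo experience still ends at about Week 12, so the revised tables remain descriptive beyond that point.

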3.3. Strata and Covariates

Subjects will be randomly assigned to treatment groups via the interactive voice or web response system (IXRS) in a 2:2:1 ratio to lanraplenib 30 mg, filgotinib 200 mg and placebo using a stratified randomization schedule. Stratification will be based on the following variables:

- Disease subtype (chronic cutaneous lupus erythematosus [CCLE] vs subacute cutaneous lupus erythematosus [SCLE])
- Concurrent background systemic disease-modifying antirheumatic drug [DMARD] use

For the stratification, systemic DMARDs administration will be considered. If there are discrepancies in stratification factor values between the IXRS and the clinical database, the values recorded in the clinical database will be used in the analyses. If it is impossible to derive the stratification factor from the clinical database due to missing values then the data from IXRS will be used.

Efficacy endpoints will be evaluated using stratification factors as covariates or stratification variables for analyses, as specified in Section 6.

For efficacy endpoints, the baseline value of the efficacy variable(s) will be included as a covariate in the efficacy analysis model.

3.4. Examination of Subject Subgroups

The primary and secondary efficacy endpoints will be examined using the following subgroups:

- Age (< 50 years and \geq 50 years)
- Disease subtype (CCLE, SCLE)
- Concurrent background disease-modifying antirheumatic drug [DMARD] use at baseline (Yes, No)
- Concurrent use of systemic (oral) corticosteroids at baseline (Yes, No)
- Diagnosis of SLE (Yes, No)
- Duration of the disease (<10 years, \geq 10 years)
- Baseline CLASI-A (<15, \geq 15)

The descriptive statistics for each treatment group within the corresponding subgroup will be provided.

3.5. Multiple Comparisons

All significance testing will be done at the significance level of 0.1 with no multiplicity adjustment in this proof-of-concept study, unless otherwise specified.

3.6. Missing Data and Outliers

3.6.1. Missing Data

In general, missing data will not be imputed unless methods for handling missing data are specified. Exceptions are presented in this document.

For missing last dosing date of study drug, imputation rules are described in Section 4.2.1. The handling of missing or incomplete dates for AE onset is described in Section 7.1.5.2, and for prior and concomitant medications in Section 7.4. Imputation rules adopted in the efficacy analyses are specified in Section 6.

3.6.2. Outliers

Outliers will be identified during the data management and data analysis process, but no sensitivity analyses will be conducted. All data will be included in the data analysis.

3.7. Data Handling Conventions and Transformations

In general, age (in years) on the date of the first dose of study drug will be used for analyses and presentation in listings. If an enrolled subject was not dosed with any study drug, the randomization date will be used instead of the first dosing date of study drug. For screen failures, the date the informed consent was signed will be used for age calculation. If only the birth year is collected on the CRF, “01 July” will be used for the unknown birth day and month for the purpose of age calculation. If only birth year and month are collected, “01” will be used for the unknown birth day.

Non-PK data that are continuous in nature but are less than the lower limit of quantitation (LOQ) or above the upper LOQ will be imputed as follows:

- A value that is 1 unit less than the LOQ will be used to calculate descriptive statistics if the datum is reported in the form of “ $< x$ ” (where x is considered the LOQ). For example, if the values are reported as < 50 and < 5.0 , values of 49 and 4.9, respectively, will be used to calculate summary statistics. An exception to this rule is any value reported as < 1 or < 0.1 , etc. For values reported as < 1 or < 0.1 , a value of 0.9 or 0.09, respectively, will be used to calculate summary statistics.
- A value that is 1 unit above the LOQ will be used to calculate descriptive statistics if the datum is reported in the form of “ $> x$ ” (where x is considered the LOQ). Values with decimal points will follow the same logic as above.
- The LOQ will be used to calculate descriptive statistics if the datum is reported in the form of “ $\leq x$ ” or “ $\geq x$ ” (where x is considered the LOQ).

Natural logarithm transformation will be used for plasma/blood concentrations and analysis of PK parameters. Plasma concentration values that are below the limit of quantitation (BLQ) will be presented as “BLQ” in the concentration data listing. Values that are BLQ will be treated as 0 at predose time points, and one-half the value of the LOQ at postbaseline time points.

The following conventions will be used for the presentation of summary and order statistics:

- If at least 1 subject has a concentration value of BLQ for the time point, the minimum value will be displayed as “BLQ.”
- If more than 25% of the subjects have a concentration data value of BLQ for a given time point, the minimum and Q1 values will be displayed as “BLQ.”
- If more than 50% of the subjects have a concentration data value of BLQ for a given time point, the minimum, Q1, and median values will be displayed as “BLQ.”
- If more than 75% of the subjects have a concentration data value of BLQ for a given time point, the minimum, Q1, median, and Q3 values will be displayed as “BLQ.”
- If all subjects have concentration data values of BLQ for a given time point, all order statistics (minimum, Q1, median, Q3, and maximum) will be displayed as “BLQ.”

PK parameters that are BLQ will be imputed as one-half LOQ before log transformation or statistical model fitting.

3.8. Analysis Visit Windows

3.8.1. Definition of Study Day

Study day will be calculated from the first dosing date of study drug and derived as follows:

- For post dose study days: Assessment Date – First Dosing Date + 1
- For days prior to the first dose: Assessment Date – First Dosing Date

Therefore, Study Day 1 is the day of the first dose of any study drug.

For placebo subjects who were re-randomized to active treatment at Week 12, the On-Active-Treatment study day will be calculated as: Assessment Date – Date of the first dose of active treatment + 1. The date of the first dose of the study drug dispensed at Week 12 is recorded on CRF.

3.8.2. Analysis Visit Windows

The target study days for analysis visits are provided in the [Table 3](#) below:

Table 3. Target Days for Analysis Visits

Nominal Visit	Nominal Study Day/ Study Day on Active Treatment
Screening	< 1
Baseline	<=1
Week 2	15
Week 4	29
Week 8	57
Week 12	85/1
Week 14	99/15
Week 16	113/29
Week 20	141/57
Week 24	169/85
Week 30	211/127
Week 36	253/169
Week 42	295/211
Week 48	337/253
Follow-up Visit	NA

The nominal visit as recorded on the CRF will be used when data are summarized by visit.

Any data recorded under unscheduled visits will not be assigned to a particular visit or time point. However, the following exceptions will be made:

- An unscheduled visit prior to the first dosing of study drug may be included in the calculation of the baseline value, if applicable
- Unscheduled visits after the first dose of study drug will be included in determining the maximum postbaseline toxicity grade in safety analyses.

For subjects who prematurely discontinue from the study, early termination (ET) data will be assigned to what would have been the next scheduled visit where the respective data were scheduled to be collected.

Data collected at a follow-up visit will be summarized as a separate visit, and labeled “Follow-up Visit.”

Data obtained after the follow-up visit or last dose date plus 30 days (whichever is later) will be excluded from the summaries, but will be included in the listings.

3.8.3. Selection of Data in the Event of Multiple Records in an Analysis Visit

Depending on the statistical analysis method, single values may be required for each analysis window. For example, change from baseline by visit usually requires a single value.

If multiple valid, nonmissing, continuous measurements are recorded for the same visit, records will be chosen based on the following rules if a single value is needed:

- In general, the baseline value will be the last nonmissing value on or prior to the first dosing date of study drug (Study Day 1), except for the analyses of active treatment period where the first dosing date of the active drug will be used. If multiple measurements occur on the same day, the last nonmissing value on or prior to the date of first dosing of study drug will be considered as the baseline value. If time is available, then use date and time to select the records with the latest time for the date. When times of these multiple measurements are not available, the average of these measurements (for continuous data) will be considered as the baseline value.
- For postbaseline values:
 - The record closest to the target day for that visit will be selected.
 - If there are 2 records that are equidistant from the target day, the later record will be selected.
 - If there is more than 1 record on the selected day and time is not collected then the average will be taken, unless otherwise specified.

If multiple valid, nonmissing, categorical measurements exist for the same visit, records will be chosen based on the following rules if a single value is needed:

- For baseline, the last available record on or prior to the date of the first dose of study drug will be selected. If there are multiple records with the same time or no time recorded on the same day, the value with the lowest severity will be selected (eg, normal will be selected over abnormal for safety electrocardiogram [ECG] findings).
- For postbaseline visits
 - The record closest to the target day for that visit will be selected
 - If there are 2 records that are equidistant from the target day, the later record will be selected.
 - If there are multiple records with the same time or no time recorded on the same day, the value with the worst severity within the window will be selected (eg, abnormal will be selected over normal for safety ECG findings).

All records will be listed by collection date.

